12 SOURCE DOCUMENTS AND ACCESS TO SOURCE DATA/DOCUMENTS

We will maintain appropriate medical and research records for this trial, in compliance with ICH E6, Section 4.9 and regulatory and institutional requirements for the protection of confidentiality of subjects. As part of participating in a DMID-sponsored, DMID-affiliated, or manufacturer-sponsored study, we will permit authorized representatives of the sponsor(s), DMID, and regulatory agencies to examine (and when required by applicable law, to copy) clinical records for the purposes of quality assurance reviews, audits, and evaluation of the study safety and progress.

Source data are all information, original records of clinical findings, observations, or other activities in a clinical trial necessary for the reconstruction and evaluation of the trial. Examples of these original documents and data records include, but are not limited to, hospital records, clinical and office charts, laboratory notes, memoranda, subjects' memory aid or evaluation checklists, pharmacy dispensing records, recorded data from automated instruments, copies or transcriptions certified after verification as being accurate and complete, microfiches, photographic negatives, microfilm or magnetic media, x-rays, and subject files and records kept at the pharmacy, at the laboratories, and medico-technical departments involved in the clinical trial. The electronic CRFs and subsequent database will be stored on a password protected computer. Other sources of data will include:

- MRI images will be stored both at QECH and on a password protected server at Michigan State University.
- ONSD images will be stored on an ultrasound machine at QECH. It is password protected and stored in a locked room adjacent to the ward.
- TCD images will be stored on an ultrasound machine at QECH. It is password protected and stored in a locked room adjacent to the ward.
- Heart rate variability data will be stored on a Malawi-based server and securely transmitted to Michigan State University where it will be available for download and analysis by co-investigators.

13 QUALITY CONTROL AND QUALITY ASSURANCE

A plan for local monitoring of clinical quality has been documented in a Clinical Quality Management Plan (CQMP) (see Manual of Operations). This document details the Standard Operating Procedures (SOPs) for on-site quality management including data evaluation methods, staff training methods, documents to be reviewed, and corrective actions to be taken should deficits be detected. This document will be reviewed annually and submitted to DMID.

All clinical observations and laboratory evaluations will be recorded in accordance with the Manual of Procedures.

Following written SOPs, the monitors will verify that the clinical trial is conducted and data are generated, documented (recorded), and reported in compliance with the protocol, GCP, and the applicable regulatory requirements.

We will provide direct access to source data/documents, and reports for the purpose of monitoring and auditing by the sponsor, and inspection by local and regulatory authorities.

The Data Manager will implement quality control procedures beginning with the data entry system and generate data quality control checks that will be run on the database. Any missing data or data anomalies will be communicated to the site for clarification/resolution.

The PI is responsible for ensuring that routine quality management activities are conducted.

14 ETHICS/PROTECTION OF HUMAN SUBJECTS

14.1 Ethical Standard

The principal investigator (PI) will ensure that this study is conducted in full conformity with the current revision of the Declaration of Helsinki, or with the principles set forth in The Belmont Report: Ethical Principles and Guidelines for the Protection of Human Subjects of Research of the US National Commission for the Protection of Human Subjects of Biomedical and Behavioral Research (April 18, 1979) and codified in 45 CFR Part 46 and/or the ICH E6; 62 Federal Regulations 25691 (1997), whichever affords the greater protection to the subject.

14.2 Institutional Review Board

Each participating institution must provide for the review and approval of this protocol and the associated informed consent documents and recruitment material by an appropriate independent ethics committee (IEC) or IRB registered with the OHRP. Any amendments to the protocol or consent materials must also be approved before they are placed into use. In the United States and in other countries, only institutions holding a current US Federal-Wide Assurance issued by OHRP may participate. All activities will be reviewed by a Michigan State University IRB as well as the local IRB (the University of Malawi College of Medicine Research and Ethics Committee [COMREC]).

14.3 Informed Consent Process

Informed consent is a process that is initiated prior to the individual's agreeing to participate in the study and continuing throughout the individual's study participation. Extensive discussion of risks and possible benefits of this therapy will be provided to caregivers of subjects. Consent forms describing in detail the study interventions/products, study procedures, and risks are given to the caregiver and written documentation of informed consent is required prior to starting intervention/administering study product. Consent forms will be IRB-approved and the caregiver will be asked to read and review the document. Upon reviewing the document, the nurse initiating informed consent will explain the research study to the subject and answer any questions that may arise. Caregivers will sign the informed consent document prior to any procedures being done specifically for the study. They will have the opportunity to discuss the study with their surrogates or think about it prior to agreeing to participate. Caregivers may withdraw consent at any time throughout the course of the trial. A copy of the informed consent document will be given to the caregivers for their records. The rights and welfare of study subjects will be protected by emphasizing to caregivers that the quality of their child's medical care will not be adversely affected if they decline to participate in this study.

14.4 Detailed Informed Consent Process

There are two consent processes potentially involved in this study:

1. Consent for screening. This is the first step for all patients, and the ONLY step for patients who do not have increased brain volume on MRI. These study participants will spend the first 24 hours on the PICU or the PRW (for continuous monitoring for HRV) and if in the PICU will then be moved to the PRW unless they deteriorate, clinically, and warrant ICU care.
2. Consent to enroll in the interventional clinical trial. This option is for patients with MRI evidence of increased brain volume on MRI

In all cases the pertinent material will be supplied in both oral and written form. Forms will be available in English and the local language, Chichewa. The caregiver will be supplied with a copy of the consent form and given ample time to ask questions regarding specifics of the study. A study clinician or study nurse will review the study consent with the parents or guardians accompanying the child. If the parent/guardian is illiterate, the consent will be explained verbally. If the parent/guardian is unable to form a signature, a thumb print will be obtained instead.

Although all subjects will be minors under the age of twelve, the subjects will not be capable of providing assent to participate because all will be, by definition, comatose.

Exclusion of Women, Minorities, and Children (Special Populations)

The major burden of malaria is borne by children; therefore, only children under the age of thirteen years will be enrolled in this study. Subjects will all be Malawian children. All children will be cared for on specially adapted pediatric wards. Parents/guardians are allowed to remain with the children throughout their hospitalization, and all meals and medications are provided without cost. The licensed clinicians providing care are all trained in the management of children with CM, and each research unit is amply staffed with trained dedicated nursing staff. No participant will be excluded on the basis of sex/gender or ethnicity.

14.5 Subject Confidentiality

Subject confidentiality is strictly held in trust by the participating investigators, their staff, and the sponsor(s) and their agents. This confidentiality is extended to cover testing of biological samples in addition to the clinical information relating to participating subjects.

The study protocol, documentation, data, and all other information generated will be held in strict confidence. No information concerning the study or the data will be released to any unauthorized third party without prior written approval of the sponsor.

The study monitor or other authorized representatives of the sponsor may inspect all documents and records required to be maintained by the investigator, including but not limited to, medical records (office, clinic, or hospital) and pharmacy records for the subjects in this study. The clinical study site will permit access to such records.

14.6 Study Discontinuation

In the event of the discontinuation of the study, any subject currently enrolled in the study will continue in their current study arm, unless study discontinuation was due to one arm being determined to be superior to the others. In this case, study subjects will be switched to the arm showing highest efficacy.

14.7 Future Use of Stored Specimens

Plasma, urine, and CSF samples will be stored at the study site in liquid nitrogen or at minus-80°C, filed by study number, and de- identified.

15 DATA HANDLING AND RECORD KEEPING

Clinical research data will be managed using the Research Electronic Data Capture (REDCap)²⁷⁷ web-based software application developed by Vanderbilt University and hosted on servers located at the Malaria Alert Center, Blantyre, Malawi. For the purpose of data backup, a copy of the data will be hosted by the Biomedical Research Informatics Core (BRIC) on servers at MSU. The REDCap database developed for the Study will organize patient data entered directly into the database by clinicians using the REDCap application deployed on tablets at the patient bedside, by hospital staff using paper data collection forms, and by hospital staff and radiologists using computers for file uploads of MRI and laboratory results. The goals of the Data Management Plan are to optimize workflow for the capture of high quality data, provide a well-documented data audit trail, deliver robust measures of data security, and facilitate easy data access and data sharing for the Study research team.

15.1 Data Management Responsibilities

Roles for data management will engage various members of the study research team and will be supported by REDCap functionality. The PI will have access to all study data, and access to by other study personnel will be restricted as directed by the PI. REDCap user definitions and user permissions, which allow for role-based and form-level access permissions and restrictions, will be used to limit access to identifying information only to necessary individuals. Data exports will be configured to remove identifying information by shifting date fields and redacting all other fields marked as identifying, as determined by the PI. The Malawi Data Manager and BRIC Data Manager (DM) will be responsible for issues related to data collection and data quality and will train clinicians and other hospital staff on matters related to direct electronic data capture. The BRIC Project Supervisor and Development Supervisor will oversee and ensure implementation and monitoring of the data management plan. They will work closely with the PI, and Study team to ensure that the informatics configuration, testing, and production processes are adequately documented. They will meet regularly to review data quality.

15.2 Data Capture Methods

Data Collection

Clinical research data will be managed using a REDCap Study database and customized features to support the entry of patient data, using tablets at the patient bedside. A majority of the clinical trial data will be entered directly into the database by clinicians and other hospital staff as the data are generated. The appropriate patient database record will be queued for direct electronic data capture by the use of barcodes, which will encode the patient Study ID#. Biologic specimens and paper data collection forms used for data capture will be labeled with barcodes to identify the associated patient. Persons entering data via the tablet will require an active REDCap account username and password and/or pin-authentication, and users will be logged out after a period of inactivity. REDCap allows tracking of form data entry through a form status dashboard, and each form can be signed electronically after it is moved to a 'completed' status. In case of power failure, back up paper forms will be stored in locked file cabinets.

Corrections to data on paper forms will be initialed and dated, and the data error will be overwritten with a single strike-through line.

During transmission of data, REDCap uses Secure Hypertext Transfer Protocol (HTTPS) which employs a standard Secure Sockets Layer (TLS 1.0, 1.1, 1.2 - 128 bit block size) encryption technology. SSL creates the secure connection and HTTPS transmits the data securely. All subject data will eventually reside in a MySQL database server. The REDCap application includes functionality to enable 21 CFR part 11 compliance for electronic records and signatures, including a comprehensive audit log that records all user activity. Audit logs are created automatically within the REDCap application to capture the complete user history of database activity.

The final record for each study participant will comprise data collected over a period of two years: from initial data collection during hospitalization through and 6-month periodic follow-up assessments to 12-months post-randomization

Data Quality

The Malawi and MSU-BRIC DMs will work together to provide ongoing management and review of data collection processes and data quality. The MSU-BRIC DM will provide on-site initial data entry training for study personnel, and refresher trainings via annual trips. During active enrollment periods, the Malawi and MSU-BRIC DMs will conference weekly to address matters related to data entry and data quality. DMs will utilize standard REDCap features to ensure data integrity and quality. Variables will be designed with real-time field validation rules, and data will be reviewed using built-in checks for missing values and outliers. The Data Quality module will be used to execute quality control verification on all fields and to resolve discrepant data, using an audited trail of query and query resolution.

Data Security

REDCap will be hosted on a server housed in a locked and climate-controlled server room at the Malaria Alert Centre, Blantyre, Malawi. The server resides on its own private segment of the network, protected through a firewall, which routes traffic as well as provides active intrusion detection and protection. Data will be accessed through an HTTPS connection to the web application front end. Daily backups of the data are made to an alternate storage location at an off-site location to protect data in the event of a disaster that destroys the server room. A back-up copy of the Malawi REDCap study database will be maintained by MSU-BRIC, which is described in detail in the Project/Performance Site(s) and Resources section of the application. The backup of the Malawi REDCap study database will be purely file level backup and not generally available through a web interface. In the event that the service is unavailable in Malawi, BRIC will enable access to the backup copy and it will follow the same terms of service as the MSU- REDCap server. The MSU- REDCap server is housed in a facility which satisfies requirements for the storage of Health Insurance Portability and Accountability Act (HIPPA) data. The server is connected to a private segment of the BRIC network. The segment is protected through a firewall, which routes traffic and provides active intrusion detection and protection. Security staff patrols, key card access, and audio/video monitoring protect the

physical location of the server. Daily and monthly backups of the database are made and retained on a server for fast restore capabilities. Copies of the data are moved to tape daily and transported to a separate storage location. Tapes rotate after 28 days.

15.3 Types of Data

The final record for each study patient will comprise data collected during hospitalization for acute cerebral malaria and neurological assessment data collected at follow-up visits 1, 3, 6, and 12 months post-randomization. These data will include MRI images and patient clinical data collected during the course of care and intervention, and neurological and developmental assessments.

15.4 Timing/Reports

Data will be extracted for QC/QA on an annual basis (at a minimum of every 30 subjects). In addition to presenting key study outcome data, reports will consider internal data management of data quality, the timely use of data entry and cleaning, and the study enrollment schedule. The content and frequency of study quality and operational metric reports will be defined by the Project Manager. Study metric reports will be interpreted to identify the need for corrective action such as training or re-training, modification of the protocol, or modification of data collection material.

15.5 Study Records Retention

Study records in the format of paper and electronic versions are to be retained by the Malawi Data Management Unit (DMU) at the College of Medicine for a minimum of 2 years after the submission of the final report and close-out procedures. A longer retention period can be arranged in accordance with NIAID requirements. No records will be destroyed without the written consent of the sponsor, if applicable. It is the responsibility of the NIAID to inform the investigator when these study records no longer need to be retained. The retention of the original study records shall be the responsibility of the principal investigator.

REDCap is designed to export data easily in formats ready for analyses in a number of standard statistical software applications. For long term storage, data will be preserved in comma-separated-value file format. Data will be preserved in the REDCap database for approximately one-year following the cessation of active data collection. The PI will be provided with metadata and the final de-identified dataset. After obtaining the PI's release signature, live data will be removed the server, and backup files will be phased out systematically as tapes are retired. The PI will serve as the primary contact for access and questions regarding the data collected for the Study.

15.6 Protocol Deviations

A protocol deviation is any noncompliance with the clinical trial protocol, Good Clinical Practice (GCP), or protocol-specific Manual of Procedures (MOP) requirements. The noncompliance

may be either on the part of the subject, the investigator, or the study site staff. As a result of deviations, corrective actions are to be developed by the site and implemented promptly.

These practices are consistent with GCP:

- 4.5 Compliance with protocol, sections 4.5.1, 4.5.2, and 4.5.3
- 5.1 Quality Assurance and Quality Control, section 5.1.1
- 5.20 Noncompliance, sections 5.20.1, and 5.20.2.

It is the responsibility of the site PI/study staff to use continuous vigilance to identify and report deviations within 5 working days of identification of the protocol deviation, or within 5 working days of the scheduled protocol-required activity. All deviations will be promptly reported to DMID, via the TRI/ICON DMID-Clinical Research Operations and Management Support (CROMS) email ([contact]), web- (www.dmidctm.com) or fax-based system ([name]). All deviations from the protocol must be addressed in study subject source documents. A completed copy of the DMID Protocol Deviation Form (TRI/ICON DMID-CROMS or IDES form) will be maintained in the regulatory file, as well as in the subject's source document. All deviations will be reported to the local ISM quarterly, and to the IRBs at Michigan State University and the University of Malawi College of Medicine annually, unless advised otherwise by the local ISM.

16 PUBLICATION POLICY

Following completion of the study, the investigators will publish the results of this research in a scientific journal. In accordance with the International Committee of Medical Journal Editors (ICMJE) member journals, the trial will be registered in a public trials registry such as ClinicalTrials.gov, which is sponsored by the National Library of Medicine. It is the responsibility of DMID to register this trial in an acceptable registry. Financial support from NIAID will be acknowledged in all publications.

The primary manuscript will be developed by the PI in conjunction with other Key Personnel.

All publications emanating from this protocol will be submitted to the digital archive PubMed Central upon acceptance for publication, as required by the US National Institutes of Health Access Policy (Division G, Title II, Section 218 of PL 110-161 (Consolidated Appropriations Act, 2008)). PubMed Central reference numbers (PMIDs) will be attached to citations of all manuscripts in all progress reports required for the study described with this protocol.

18 PROTOCOL APPENDICES

Appendix A	Schedule of Events
Appendix B	Adverse Event Grading Table

Appendix A

Schedule of Events

Clinical and Laboratory Evaluations

A = performed on all children on PRW/PICU [(A) = only if still unconscious]

S = performed on children eligible to be screened for TBS study

I = performed as part of TBS trial [(I) = only if still unconscious]

Event	Admission	Screening	With TBS consent	Day 1	Day 2	Days 3 -7	Follow-up visits
History	A						A
Physical Exam	A			A,A	A,A	A,A	A
Vital signs	A			A – q2 hours	A – q2 hours	A – q2 hours	A
IV anti-malarial Rx	A			A,A	A,A		
PO anti-malarial Rx						A (3 day course)	
MP and PCV	A			A A A A	(A)(A) (A)(A)	(A)(A) (A)(A)	A
Lactate and glucose check	A			A A A A	(A)(A) (A)(A)	(A)(A) (A)(A)	
Lumbar Puncture	A						
Retinal exam		S		(I,)	(I,)	(I,)	
MRI		S		I	(I)	(I)	I (1 month)
NIRS		S		I	I	I	I (1 month)
TCD		?	I?	I	I	I	I (1 month)
ONSD			I	I,	(I,)	(I,)	I
Expanded neurologic exam			I	I, I	(I,I)	(I,I)	I
Heart rate variability			I	I	I	I	
Lung ultrasound			I	I	I	I	
Brain swelling intervention			I	I	I	I	

Appendix B - Adverse Event Table

Event	Grade 1	Grade 2	Grade 3	Grade 4
Hypernatremia	166-170 mEq/L	171-180 mEq/L	181-190 mEq/L	>191 mEq/L
Hyperkalemia	5.4-5.9mEq/L	6.0-6.4mEq/L	6.5-7.0mEq/L	> 7.0 mEq/L
Hypokalemia			2.0-2.4 mEq/L	< 2.0 mEq/L
Phlebitis	erythema \geq 2 cm diameter at IV site without swelling, venous cord or fever	erythema and induration \geq 2 cm diameter at IV site without venous cord or fever	erythema and induration \geq 2 cm diameter at IV site with venous cord or fever \geq 38°C	erythema and induration \geq 2 cm diameter at IV site with venous cord and fever \geq 38°C
Pneumothorax	NA	small pneumothorax with no cardiovascular effect -no intervention required	small pneumothorax requiring placement on 100% oxygen	pneumothorax with associated cardiovascular compromise requiring needle decompression or placement of chest tube
Pneumomediastinum	NA	simple pneumomediastinum-asymptomatic (No intervention required)	pneumomediastinum with extrathoracic subcutaneous emphysema (no intervention required)	pneumomediastinum with associated cardiovascular compromise requiring placement of drain or surgical intervention
Subglottic stenosis	Need for racemic epinephrine(X 1 dose)use post-extubation	Need for use of multiple doses of racemic epinephrine	Need for reintubation secondary to respiratory difficulty	Need for surgical resection of subglottic stenosis and/or tracheostomy secondary to sub glottic stenosis
Respiratory nosocomial infection	Post-admit pneumonitis on CXR and phys exam with O2 sat of \geq 90% on room air	Post-admit pneumonitis on CXR and phys. Exam with O2 sat of < 90% on RA, O2 sat \geq 90% on supplemental 02	Post-admit pneumonitis on CXR and phys. exam after admission with O2 sat < 90% on room air, O2 sat 70-90% with supplemental 02	Post-admit pneumonitis on CXR and phys exam with O2 sat of < 90% on room air, O2 sat < 70% with supplemental 02
Hypotension		Reduction of resting mean arterial blood pressure 25-49% of pre-intubation mean arterial pressure	Reduction of resting mean arterial blood pressure 50-74% of pre-intubation mean arterial pressure	Reduction of resting mean arterial blood pressure >75% of pre-intubation mean arterial pressure
Endotracheal tube obstruction	Binary (present or absent)			
Inadvertent endotracheal tube dislodgment				
Bradycardia induced by vagal response		Reduction of resting heart rate 25-49% of pre-intubation heart rate	Reduction of resting heart rate 50-74% of pre-intubation heart rate	Reduction of resting heart rate >75% of pre-intubation heart rate

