3. Increased blood flow volume: The anemia, fever and seizures⁸⁷ that are commonly seen in CM patients may lead to increased cerebral blood flow volume (hyperemia) and dysfunction of autoregulatory systems⁸⁸.
4. Vascular congestion: Intense sequestration of parasitized red cells in postcapillary venules may lead to venous obstruction and vascular congestion^{89, 90}.

The current standard of care on the Paediatric Research Ward in Blantyre addresses the likely determinants of increased blood flow volume (seizures, fever and anemia). Potential interventions were reviewed to identify those most likely to address the other three putative etiologies: vasogenic edema, cytotoxic (cellular) edema and vascular congestion.

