6.11 Concomitant Medications/Treatments

While on the PICU/PRW, all participants will receive standard of care anti-malarial treatment. This includes the following:

- Anti-malarial treatment: Artesunate will be administered according to national treatment guidelines upon admission, at 12- and 24-hours post-admission, and once a day thereafter until the child is able to take oral medication, or for a total of 5 days. After the child is able to take oral medications, they will be prescribed Co-Artem® (a fixed dose combination tablet containing artemether, 20 mg and lumefantrine, 120 mg). Dosing will be weight-based according to national treatment guidelines. Oral therapy is for three days.
- Antipyretics: An aggressive fever control regimen will be undertaken in both arms – as pyrexia has been shown to be a major predictor of poor outcome in TBI participants²⁵². Anti-pyretic therapy will be initiated for any temperature $>38^{\circ}\text{C}$. The two components will be:
 - Paracetamol – 25mg/kg per rectum (PR) loading dose and 15 mg/kg PR Q6 hours thereafter
 - Ibuprofen – 10mg/kg per naso-gastric tube (PNGT) Q6 hours

Therapy will be initiated with paracetamol. If euthermia is not achieved in 3 hours, ibuprofen will be added. The two modalities may be scheduled on alternating Q6 hour regimens, at the discretion of the intensivist.

- Anti-convulsants: Locally available anti-convulsants include paraldehyde, diazepam, phenobarbital, and phenytoin. Choice of a specific anti-convulsant is determined on a participant-to-participant basis based on the duration of seizures, available routes of administration, and other clinical characteristics (e.g., respiratory status) of the participant.
- Antibiotics: Participants initially unable to undergo lumbar puncture to rule out meningitis will be placed on ceftriaxone (100mg/kg IV, daily) until a lumbar puncture can be performed or for a maximum of seven days, whichever comes first. A blood culture will be collected initially on all patients, and appropriate antibiotics will be prescribed on the basis of a positive culture. Participants with fever refractory to anti-malarials will have a second venous blood sample collected for culture and the initiation of empiric antibiotic treatment until culture results are available. Continued antibiotic administration will be dependent on blood culture results and clinical status. See Section 6.2.5 for antibiotic therapy for intubated patients who develop a nosocomial pneumonia.

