9.2.1.3 Expected Adverse Events

All adverse events meeting the criteria listed above will be collected. Special concern will be paid to the following adverse events as they are known side effect of the investigational drugs:

- Potentially attributable to the hypertonic saline intervention:
 - Hypernatremia
 - Hypokalemia
 - Hyperkalemia
 - Phlebitis
- Potentially attributable to the intubation intervention:
 - Pneumothorax
 - Pneumomediastinum
 - Subglottic stenosis
 - Stridor
 - Tracheostomy
 - Bronchospasm
 - Pulmonary hemorrhage

- Respiratory nosocomial infections
- Hypotension
- Endotracheal tube obstruction
- Inadvertent endotracheal tube dislodgment
- Bradycardia induced by vagal response

Adverse Event grading tables (attached as Appendix B) will be used to define these conditions. These events will be captured in the CRF and subsequently in tabular format, listing time of event onset, time of event resolution, brief description of the event, clinician's assessment of severity, and clinician's assessment of relation to the intervention. They will be reported to the local ISM on a monthly basis, and an annual report of these events will be presented to the DSMB, as well as both IRBs. The events will be captured for the duration of the participants' stay on the PICU/PRW, independent of whether the participant is still receiving interventional therapy.

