9.5 Halting Rules

The following eventuality would trigger temporary suspension of enrollment until a safety review is convened and further evaluation undertaken:

- Five subjects where current HPS regimen is unable to achieve the target Na⁺ levels of 150-160 mmol/L.
- Any SAE deemed to be related to each of the experimental medical interventions (ventilator support or infusion of 3% hypertonic saline solution).

DMID retains the authority to suspend additional enrollment and study interventions during the entire study, as applicable.

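### Appendix B grades phlebitis partly on fever, which malaria itself causes, so in a febrile child erythema alone has no grade and indurated sites move up one grade

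*Combined protocol and SAP*

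**What the plan says.** Section 9.2.1.3 lists phlebitis among four events potentially attributable to hypertonic saline. It makes Appendix B the operative scale: "Adverse Event grading tables (attached as Appendix B) will be used to define these conditions".

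The Appendix B phlebitis row reads:

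- Grade 1: erythema of at least "2 cm diameter at IV site without swelling, venous cord or fever".
- Grade 2: erythema and induration of at least "2 cm diameter at IV site without venous cord or fever".
- Grade 3: erythema and induration of at least "2 cm diameter at IV site with venous cord or fever" of 38°C or more.
- Grade 4: erythema and induration of at least "2 cm diameter at IV site with venous cord and fever" of 38°C or more.

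The protocol expects fever from the disease. Section 2.1.2 describes falciparum infection as febrile. Section 2.2 describes "The anemia, fever and seizures" as common in cerebral malaria patients. Section 6.11 states that "An aggressive fever control regimen will be undertaken in both arms", starting above 38°C. Section 4 makes 24 afebrile hours a condition of discharge.

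**The concern.** A severity grade for a complication at the infusion site should separate worse sites from milder ones. Here the step between grades can be taken by body temperature alone, in a population whose admission illness produces fever. Two children with the same vein findings receive different grades, or one of them none, according to whether malarial fever is present that day.

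What is at stake is how far the phlebitis severity table can be trusted. Safety of hypertonic saline is a secondary objective (Section 3.1), and Section 9.2.1.3 sends these events monthly to the independent safety monitor and annually to the DSMB and both IRBs. A comparison with usual care may not cancel the distortion. Phlebitis is listed only against hypertonic saline, and Section 9.2.1 says both that only events possibly attributed to the intervention are collected and that all events are documented.

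**Working it through.** There is no planned figure to reproduce. The check applies the four written definitions to every combination of local signs and temperature.

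**Inputs.** The four Appendix B definitions above. Erythema of at least 2 cm is taken as present, any induration is taken to meet the 2 cm size, and the swelling excluded in Grade 1 is treated as the same sign as induration. Because Grades 1 and 2 exclude fever without giving a threshold, a band of 37.6–37.9°C was added as an assumption and counted as fever for those two grades only.

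**Rules.**

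- Grade 1 = erythema, no induration, no cord, no fever.
- Grade 2 = erythema, induration, no cord, no fever.
- Grade 3 = erythema, induration, and (cord or temperature ≥38°C).
- Grade 4 = erythema, induration, cord, and temperature ≥38°C.

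**Results.**

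| Local signs (with erythema ≥2 cm) | Afebrile | 37.6–37.9°C, if called fever | ≥38°C |
|---|---|---|---|
| No induration, no cord | 1 | none | none |
| Induration, no cord | 2 | none | 3 |
| Induration and cord | 3 | 3 | 4 (also meets 3) |
| Cord, no induration | none | none | none |

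Reading across the rows:

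1. At 38°C or above, Grades 1 and 2 cannot be reached. The first local picture loses its grade, and the next two each rise by one.
2. If a temperature just under 38°C counts as fever, induration without a cord also falls between Grade 2 (fever excluded) and Grade 3 (38°C not reached).
3. A cord without induration has no grade at any temperature. This gap is separate from the fever problem, but it sits in the same row.

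**Does another rule repair this?**

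- The baseline rule in Section 9.2.1 decides whether a condition present at screening is an adverse event. It does not tell the grader to ignore baseline fever when scoring a new phlebitis.
- The malaria-attribution rule in Section 9.2.3 decides which events are graded and reported. It does not say how fever counts within a grade.
- The general four-level scale in Section 9.2.1.1 is for events that are not protocol-specific. Phlebitis is protocol-listed and is sent to Appendix B.

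None of the three discounts malarial fever. Other Appendix B rows do allow for the child's prior state: hypotension and bradycardia are graded against the pre-intubation value, and respiratory infection must arise after admission.

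**The case against.** The strongest case on the other side is that little follows from the grade.

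- **Consequences.** A reader might infer that an inflated Grade 4 counts as life-threatening, hence as an SAE, and so suspends enrolment under Section 9.5 ("Any SAE deemed to be related to each of the experimental medical interventions"). The documents do not support that chain. The scale with a life-threatening level (Section 9.2.1.1) is for other events. SAE status (Section 9.2.3) rests on outcome and medical judgment, not grade. Section 9.2.1 limits SAE reporting to events in Section 2.4.1.2 or unanticipated ones; Section 2.4.1.2 omits phlebitis, which Section 9.2.1.3 lists as expected. The Grade 4 language in Section 6.3 concerns laboratory values, and the response to phlebitis in Section 9.2.4.3 does not vary by grade. This part of the objection stands in full.
- **Lost events.** A reader might infer that mild episodes vanish from the record. Section 9.2.1.3 has the CRF capture onset, resolution, a brief description, and the clinician's view of severity and relation. An episode that fits no cell can still be recorded. What is lost is its grade, although the statement that Appendix B defines the condition leaves some ambiguity.
- **Frequency.** Section 9.2.4.3 links phlebitis to prolonged infusion, Section 6.11 treats fever promptly, and Section 2.3 says 85% of ward patients have died or been discharged within 72 hours. Overlap of fever and phlebitis may therefore be less common than it first appears. That is fair, and it bears on the count, not on the rule.
- **Design choice.** Fever can be a legitimate sign of a site complication, and nothing in the documents shows it to be uninformative. This also stands. The criticism is that the table does not separate such fever from malarial fever.

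**Conclusion.** The point holds as a defect in one row of the adverse event table. For three of the four local pictures examined, the grade changes or disappears at 38°C or above with no change in the vein. This follows from the wording alone and needs no assumed rates.

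Its reach is limited to the severity labels in the hypertonic saline safety tables and the reports built on them. Phlebitis is not an outcome in Table 8, and the primary analysis, randomization, dosing and halting rules are untouched.

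The number of affected events cannot be estimated. It is tempting to multiply the 32 projected hypertonic saline children (Section 4) by guessed rates. With a cord in 5–15% and concurrent fever in 30–80%, the expected number of Grade 4 events runs from 32 × 0.05 × 0.30 = 0.48 to 32 × 0.15 × 0.80 = 3.84. That eightfold range comes entirely from the guesses, since the documents give neither rate, and it also presumes that every cord event has qualifying erythema and induration. It should not be used to size the problem.

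The conclusion rests on a literal reading of Appendix B. Graders may already be setting malarial fever aside, but no written rule tells them to.

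**What to change.** Reword the phlebitis row:

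- Grade 1: erythema of at least 2 cm.
- Grade 2: erythema with induration of at least 2 cm.
- Grade 3: erythema with a venous cord, with or without induration. This also closes the gap for a cord without induration.
- Grade 4: keep the present local signs, and count fever of 38°C or above only when the clinician judges it not attributable to malaria. Section 9.2.3 already uses that attribution principle.

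Re-grade recorded events where the CRF description includes the local signs, and list the remainder as not re-gradable. The Section 4 projection places 3 hypertonic saline children in 2018–2021 and 14 + 15 = 29 of 32 in 2022–2023, so the sooner the row is changed, the fewer events need re-grading.

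The cost is a wording change and a short re-grade, with no new data collection. A few more mild events will be counted in the hypertonic saline arm, and some past events will stay ungraded because a brief description may not mention induration or a cord. An indurated site without a cord, but with a fever the clinician attributes to the site, would be Grade 2 where it is now Grade 3. The attribution call is also a judgment in an unblinded trial, so its basis should be recorded with the grade.
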